#### **11.7 Safety Analysis**

The safety sample will include all patients exposed to the study drug.

Toxicity frequency will be tabulated by grade across all dose levels and cycles for all patients in the safety sample, and for the subset treated at the recommended Phase 2 dose. These tables will be produced at 3 time points:

1. At the end of the Phase 1b study.
2. At the Phase 2 interim analysis.
3. At the Phase 2 final analysis.

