	
Alpha-Fetoprotein (AFP)
 
HBsAg; HCV Ab; (if unknown)
 
Viral Load (if either or both HBsAg or HCV Ab are positive)
 
PK/PD sVEGF-2 Sampling
 
Immune Biomarker Sampling
 
ECOG Performance Status
 
Electrocardiogram
 
CT Scan (within 4 weeks)
 
Adverse Events

Statistical Analysis
	
Sample Size Determination: Sample size for the Phase 1 portion depends on the unknown dose-toxicity profile. For the Phase 2 portion, with <math>\alpha = 0.05</math>, assessment of 37 patients gives 80% power to detect minimum 20 percentage point improvement in the 24 week PFS response rate, assuming a 50% rate under the standard of care.
 
Randomization: No randomization is required.
 
Efficacy Analysis: Primary interest is in the PFS response rate 24 weeks after enrollment. The response rate will be described by binomial proportion estimates and 95% confidence intervals. All enrolled patients will be included in this primary analysis.
 
Safety Analysis: Adverse events will be tabulated. AE rates will be described using binomial proportions and 95% confidence intervals.

**Subject Name: (Network Sites use Initials)** \_\_\_\_\_

**Medical Record No.: (Network Sites use Subject ID#)** \_\_\_\_\_

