### 9.1.3 Reporting Adverse Events (Network Sites see Appendix A )

**Table 7. Guidelines for Routine Adverse Event Reporting for Phase 1 Studies (Regardless of Expectedness)**

Attribution	Grade 1	Grade 2	Grade 3	Grade 4
Unrelated	X	X	X	X
Unlikely	X	X	X	X
Possible	X	X	X	X
Probable	X	X	X	X
Definite	X	X	X	X

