**Table 8. Guidelines for Routine Adverse Event Reporting for Phase 2 Studies (Regardless of Expectedness)**

Attribution	Grade 1	Grade 2	Grade 3	Grade 4
Unrelated			X	X
Unlikely			X	X
Possible	X	X	X	X
Probable	X	X	X	X
Definite	X	X	X	X

Routine AEs occurring between the start date of intervention until 30 days after the last intervention or until the event has resolved, the study patient is lost to follow up, the start of a new treatment, or until the study investigator assesses the event(s) as stable or irreversible, will be reported. New information will be reported after it is received.

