**Network Sites, see Appendix (A) for information regarding, Unanticipated Problem reporting.**

### 9.4 Investigator Reporting: Notifying the Study Sponsor

Adverse events, both serious and non-serious, and deaths that occur during the patient’s study participation (from time of the first dose of tivozanib, written informed consent through 30 days after receiving the last dose of tivozanib hydrochloride) will be documented. All subjects receiving at least 1 dose of tivozanib hydrochloride, whether completing the treatment period or not, should be followed for 30 days after the last dose of tivozanib hydrochloride. New AEs and changes in ongoing AEs or those with an unknown outcome must be followed for 30 days after the last dose of tivozanib hydrochloride. All SAEs should be monitored until they are resolved or are clearly determined to be due to a patient’s stable or chronic condition or intercurrent illness(es). The Investigator will determine the seriousness, intensity, and causality of an adverse

event associated with the use of the study drug (i.e., events where there is a reasonable possibility that the event may have been caused by the study drug).

All SAEs should be recorded on a Medwatch Form 3500A and sent to the FDA (if applicable), to AVEO Pharmacovigilance/Drug Safety, to the NCCN, and to the Principal Investigator/ CRS Network Coordinators at [contact].

SAE Reporting Contact Information: please submit SAE Reports to Parexel GPPG via email ([contact]). If submission via email is not possible or delayed then submission via fax (NA [contact]) is acceptable.

Pharmacovigilance/Drug Safety  
AVEO Pharmaceuticals, Inc  
[name]  
[name]  
[contact]  
E-mail: [contact]

SAE Reporting Contact Information  
National Comprehensive Cancer Network (NCCN)  
[contact]

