## 11.3 Sample Size Determination

Between 6 and 18 patients will be enrolled in Phase 1b portion. Six Phase 1b patients treated at the recommended Phase 2 dose will be included in the Phase 2 portion of this study. An additional 31 patients will be enrolled for the Phase 2 portion of this study, for a total Phase 2 sample size of 37. This study is expected to accrue 9 patients to the Phase 1b, for a combined sample of size 40 ( $=9+37-6$ ). If 18 patients are enrolled in the Phase 1b, the maximum combined sample size is 49 ( $=18+37-6$ ).

The sample size calculation is based on testing hypotheses concerning the proportion of the treated population alive and disease free 24 weeks after enrollment. Let  $p$  represent the proportion of patients surviving with no evidence of disease progression by RECIST at 24 weeks after enrollment. A true progression rate of less than  $p_0 = 0.50$  is considered unacceptable and evidence of such will deem the treatment not worthy of further study. The null and alternative hypotheses to be tested are  $H_0: p = p_0$  versus  $H_1: p > p_0$ .

This 2-stage design requires a potential total of 37 patients to achieve approximately  $1 - \beta$  power to detect a difference of at least  $\Delta$  percentage points ( $p_0$  versus  $p_0 + \Delta$ ). For calculations in this study,  $p_0 = 0.50$ ,  $\alpha = 0.05$ ,  $1 - \beta = 0.80$  and  $\Delta = 0.20$ . With these design parameters, the sample size was calculated using the web calculator located at <http://cryptnet.net/kepner/>.

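### If Table 8 governs what is captured, pooled Grade 1-2 and any-grade AE rates are biased low, because Phase 2 patients are counted in the denominator for unrelated or unlikely low-grade events they cannot contribute

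*Combined protocol and SAP*

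**What the plan says.** Section 9.1.3 gives one guideline table per phase for routine adverse event reporting. Table 7 (Phase 1) marks Grades 1 to 4 in all five attribution rows. Table 8 (Phase 2) marks Grades 1 to 4 for possible, probable and definite, but only Grades 3 and 4 for unrelated and unlikely.

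Section 11.7 uses one denominator for both phases: "The safety sample will include all patients exposed to the study drug". On the tables it says "Toxicity frequency will be tabulated by grade across all dose levels and cycles for all patients in the safety sample". A second set is restricted to patients who received the dose chosen for Phase 2. Both are produced at the end of Phase 1b, at the Phase 2 interim and at the Phase 2 final analysis. The synopsis adds: "AE rates will be described using binomial proportions and 95% confidence intervals". Neither place splits by phase or limits by attribution.

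Section 9.4 is more general. It begins "Adverse events, both serious and non-serious, and deaths that occur during" study participation, and says these will be documented, with no restriction by grade, attribution or phase.

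**The concern.** A rate needs a numerator and a denominator that follow the same ascertainment rule. Read together, Tables 7 and 8 and Section 11.7 break this for one class of event: Grade 1-2, judged unrelated or unlikely. A Phase 1b patient with such an event counts in numerator and denominator. A Phase 2 patient with the same event would count in the denominator only.

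Any pooled row that contains these events then partly reflects the reporting rule. Its confidence interval looks too precise, because it is computed on patients who were not fully observed for that event. The mix of rules also changes between the interim and final tables, so a rate could appear to fall as Phase 2 patients accumulate.

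Safety is the first secondary objective, and Section 3.3.1 says the drug has not been tested in HCC patients. Attribution is made without a control arm, and the omitted class includes events that Section 9.1.2 calls only doubtfully related. All-cause low-grade rates therefore have some value here.

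**Working it through.** **Inputs from the documents.** Section 11.3: "Between 6 and 18 patients will be enrolled in Phase 1b portion", with 9 expected; 6 of them carried into Phase 2; 31 new Phase 2 patients; Phase 2 total 37. Section 11.2: Stage 1 has 19 patients including the carried-over ones, hence 19 − 6 = 13 new patients at the interim.

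**The plan's own totals.** Expected 9 + 37 − 6 = 40 and maximum 18 + 37 − 6 = 49, both as stated. The minimum is 6 + 37 − 6 = 37.

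**Assumptions.** Table 8 controls capture; true event rates are equal in both phases; the six carried-over patients stay under Table 7 throughout (the documents do not say). The documents give no AE rates, so every rate below is assumed.

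**Step 1: a row made up only of unrelated or unlikely Grade 1-2 events.** Expected tabulated rate = true rate × (patients under Table 7 ÷ all patients in the table).

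| Table | Share under Table 7 | Assumed true 30% shows as |
|---|---|---|
| Final, expected | 9/40 = 22.5% | 6.8% |
| Final, minimum Phase 1b | 6/37 = 16.2% | 4.9% |
| Final, maximum Phase 1b | 18/49 = 36.7% | 11.0% |
| Final, recommended-dose subset | 6/37 = 16.2% | 4.9% |
| Interim, expected | 9/22 = 40.9% | 12.3% |
| Interim, range | 6/19 = 31.6% to 18/31 = 58.1% | 9.5% to 17.4% |

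The share does not depend on the assumed rate. In the expected final table, true rates of 10% and 50% would show as 2.3% and 11.3%.

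**Step 2: an all-cause row.** Suppose 40% of patients have an event that both tables capture, and a further 10% have only an unrelated or unlikely Grade 1-2 event. The true rate is 50%. The final full-sample table would show 40 + 10 × 9/40 = 42.3%, and the subset 40 + 10 × 6/37 = 41.6%. The understatement is about 1.2-fold (50/42.3 and 50/41.6).

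**Step 3: the interval.** With assumed counts, 3 events among 9 fully observed patients is 33.3% (exact 95% CI 7.5% to 70.1%). Printed as 3 of 40 it is 7.5% (1.6% to 20.4%). In the subset, 2 of 6 is 33.3% (4.3% to 77.7%), but 2 of 37 prints as 5.4% (0.7% to 18.2%). The printed intervals are narrower, and their upper limits lie below the rate in the fully observed patients.

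**What does not change.** Grade 3-4 events, and related events of any grade, follow the same rule in both tables. The end-of-Phase-1b table contains only patients under Table 7. The DLT definition (6.2.1) uses related events of Grade 3 or higher, and the primary endpoint uses progression and death.

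**The case against.** The strongest reply is that nothing goes missing. Tables 7 and 8 are guidelines for reporting, not a specification of the case report form. Section 9.4 has serious and non-serious events documented without limit, and Table 4 schedules adverse event assessment at the visits from Cycle 1 Day 15 onward with no split by phase. If 9.4 governs, the numerator is complete and there is no dilution. This stands as far as it goes: non-collection is an inference. But 9.4 does not address the blank cells of Table 8, so the documents leave two readings open.

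A second reply is that toxicity in 11.7 means drug-related events, which both tables treat alike. Section 6.2.3 uses the word that way. However, Section 6.4 lists toxicity unrelated to treatment as a discontinuation reason, Section 6.2.1 has to add relatedness to define a DLT, and the synopsis speaks of adverse events. The restricted meaning is possible but not stated.

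Third, a reader might infer from 9/40 and 6/37 that low-grade rates in general would be understated four- to six-fold. The documents do not support that. The factor applies only to a row made up wholly of unrelated or unlikely Grade 1-2 events, and 11.7 plans no such row. All-cause rows also contain related events and are understated less, as Step 2 shows. Nor is 9 of 40 settled: Section 11.1 ties the 9 to Dose Level 2 becoming the Phase 2 dose, while Section 3.3.1 says 1 mg (Level 1) was chosen. Hence the range.

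**Conclusion.** The point holds conditionally. Sections 9.1.3 and 9.4 do not agree on what is recorded in Phase 2, and 11.7 and the synopsis pool across phases as though the rule were uniform. If Table 8 controls capture, unrelated or unlikely Grade 1-2 events would be recorded for 22.5% of the final safety sample as expected (16.2% to 36.7% over the permitted Phase 1b sizes) and for 16.2% of the recommended-dose subset. All-cause Grade 1-2 and any-grade rates at the interim and final analyses would be biased low, by an amount that depends on how much of each row is in this class.

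It would go too far to say that the events are definitely not collected, or that the safety results as a whole are unreliable. The rates that bear most on tolerability, Grade 3-4 and drug-related, are ascertained alike in both phases, and neither dose finding nor the efficacy decision is touched. The matter should be corrected before the interim and final tables are produced, but it does not threaten the design.

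**What to change.** First, reconcile 9.1.3 with 9.4: state which rule controls case report form capture in Phase 2, and which table applies to the six carried-over patients after Phase 1b. Define toxicity in 11.7 as all-cause or drug-related.

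If 9.4 controls and all events are captured, say so in 9.1.3; the pooled tables can then stay as planned.

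If Table 8 controls, limit the pooled tables and confidence intervals in 11.7 and the synopsis to events ascertained the same way in both phases: possibly, probably or definitely related events of any grade, and all events of Grade 3 or higher. Show unrelated or unlikely Grade 1-2 events in a separate table with the Phase 1b denominator only (9 if accrual is as expected; 6 in the recommended-dose subset), labelled as such.

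The cost is wording in three places and, in the second case, one extra table. No new data are needed. The separate table will have wide intervals, which is a fair statement of how few patients were fully observed for those events.

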### **11.8 Interim Analysis and Criteria for Early Termination of the Study**

No explicit interim analysis is planned for the Phase 1b dose-finding portion of the study. However, during this phase, observed toxicities will be monitored and discussed weekly by RPCI's Phase 1 Committee. Potential early termination decisions are inherent in the Phase 1 study monitoring.

The Phase 2 design includes a formal interim analysis, allowing for early termination if the experimental treatment is deemed ineffective. Early termination rules are detailed in **Section 11.2**.

## **12 CORRELATIVE DATA ANALYSIS**

### **12.1 Pharmacokinetic/Pharmacodynamic Analysis**

Using data collected from PK and PD samples, a population PK/PD model will be developed to characterize the time course of tivozanib concentrations in relation to target increases in VEGF-A and decreases in sVEGFR-2. Subsequently, diagnostic plots will be created to ascertain whether a trend exists in VEGF-A and sVEGFR-2 changes, immunological biomarker response, viral load and progression free survival (PFS). If trends exist, these endpoints will also be included in the PK/PD model. A variety of compartmental population pharmacokinetic structural models will be evaluated using a nonlinear mixed effects modeling approach, NONMEM®. The physiologic pharmacokinetic models explored will be described by the estimation of mean structural model parameters (e.g., plasma volumes of distribution and clearances), the magnitude of inter-individual variability (IIV) in these parameters, and the magnitude of residual variability (RV). The model for IIV will be assumed that the variance is proportional with respect to the typical value of the pharmacokinetic parameter, and the estimates are presented as percent coefficients of variation. This analysis will include evaluation of the influence of a limited number of patient covariates, such as patient demographics along with other patient cofactors, on the variability in select PK/PD parameters. Based on our sparse sampling approach, prior information on PK parameter estimates and variances can be used with a Bayesian estimation method to drive the model analysis. This allows for a smaller number of samples to be taken while still providing enough information to achieve sufficient model fitting. For each model, the fit will be assessed by examination of several diagnostics. For comparisons of hierarchical models, the change in the minimum value of the objective function (MVOF), a statistic that is proportional to minus twice the log likelihood of the data, will be examined. This change represents a statistic which is asymptotically distributed like  $\chi^2$ , with degrees of freedom equal to the number of parameters added to or deleted from the model. For example, a change in the MVOF of  $\geq 7.88$  between two hierarchical models represents a statistically significant difference at an  $\alpha$ -level of 0.005 for the addition of one parameter ( $df = 1$ ). The goodness-of-fit of NONMEM® analyses will be additionally assessed by examination of the following: (1) scatterplots of measured concentrations and weighted residuals versus population predicted concentrations, and weighted residuals versus time since first and last dose; (2) scatterplots of measured concentrations, individual weighted residuals, and absolute individual weighted residuals versus individual predicted concentrations; (3) the precisions of the parameter estimates

as measured by the percent standard error of the mean ( $\%SEM = \text{standard error}/\text{parameter estimate} \times 100\%$ ); (4) changes in the estimates of interindividual (IIV) and residual variability (RV); and (5) histograms, boxplots, and plots of quantiles of individual and population weighted residuals versus quantiles of the normal distribution (QQ plots).

## 12.2 Immune Biomarker

Interest is in the effect of tivozanib on several tumor-associated immune response markers. One pre- and two post-treatment measurements will be obtained from each tivozanib-treated patient who completes at least two treatment cycles. Post-treatment measurements will be obtained at Day 56, and at the end of follow up (either documented disease progression, death or one year of progression-free survival). These immune marker measurements will be presented as continuous variables.

Primary interest is in the change in immune system measurements obtained at baseline and the end of Cycle 2 (Day 56). Using (linear) mixed model methods, the change in expression measurement outcomes will be modeled against a random patient effect, and fixed-effects for time (pre vs post), patient status at Day 56 (progression/death or not) and the status-by-time interaction. Fixed effects for other exogenous effects (e.g. presence of hepatitis B/C, cirrhosis, diabetes, etc) may also be included. Mixed model methods account for the hierarchical (within patient) covariance in the outcome measurements, and missing outcome observations for patients who die/withdraw before finishing Cycle 2.

The magnitude, direction and reliability of the change estimate will be described using the fitted parameter estimate for time and its 95% confidence limits. If the immune measurements change estimate, depends on the patient status (i.e., if the status-by-time interaction is statistically significant), the change will be estimated and tested within progression strata using contrast statements.

For power calculations, we assume paired (pre/post) standardized observations are available for 37 patients, and significance threshold of 0.05. If the change in immune measurements does not depend on progression status, then this experiment can be considered as a paired t-test. This test has 80% power to detect a 0.47 standard deviation shift in mean immune measurement.

If the change in immune measurements depends on progression status, we further assume a within-patient correlation coefficient of 0.2. This ANCOVA-type model combination gives 80% power to detect a 1.6 standard deviation difference in the progression strata specific regression line slopes.

Appropriate functional forms for the mean function will be explored using means by time box plots, scatter plots, and other methods. Within-patient and time correlations will be explored using profile plots. Compliance with modeling assumptions will be assessed by examination of residual plots. PRESS residuals will be utilized to identify possible influential observations. The marker measurements may be transformed to satisfy distributional assumptions. Correlations between marker values will be tested using Spearman Rank correlation methods, and visualized using spline-augmented scatter plots.

In all, we expect a total of 8 immune measurements for each patient at each time point (four marker measurements, and four phosphorylation measurements). Methods proposed by Hochberg will be used to control the overall (family-wise) Type I error rate to 0.05.

In exploratory analyses, the three expression measurement outcomes for each patient will be modeled using (linear) mixed model methods with fixed-effects for time, cumulative dose, patient status (progressed, died, other), exogenous factors and the second order interactions with patient status. The effects of baseline expression measures on progression free and overall survival will be assessed using multivariable proportional hazards models, with adjustment for possible confounding factors. Survival distributions will be obtained using the product-limit based Kaplan Meier methods, with descriptive quantities such as median survival time and corresponding 95% confidence intervals.

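### Section 12.2 reports the immune change as the time parameter of a model that also contains status-by-time; depending on an unstated coding, that is generally not the all-patient change for which the power was calculated.

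*Combined protocol and SAP*

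**What the plan says.** Section 12.2 (Immune Biomarker) places primary interest in the change from baseline to the end of Cycle 2. No status subgroup is named.

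The model is a linear mixed model with a random term for each patient, plus "fixed-effects for time (pre vs post), patient status at Day 56 (progression/death or not) and the status-by-time interaction". The result to be reported is then fixed: "The magnitude, direction and reliability of the change estimate will be described using the fitted parameter estimate for time and its 95% confidence limits". Where the interaction is significant, "the change will be estimated and tested within progression strata using contrast statements".

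The power paragraph starts from complete data: "we assume paired (pre/post) standardized observations are available for 37 patients, and significance threshold of 0.05". It continues: "If the change in immune measurements does not depend on progression status, then this experiment can be considered as a paired t-test", with 80% power for a 0.47 SD shift. For the case where change depends on status, it assumes a within-patient correlation of 0.2 and gives 80% power for a 1.6 SD difference between strata. Eight immune measurements are covered by a Hochberg procedure at family-wise 0.05.

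The section does not state how status is coded. It does not remove the interaction when it is not significant, and it does not define a contrast averaged over status.

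**The concern.** Once a time-by-status interaction is in a model, the coefficient labelled time is no longer a main effect in the everyday sense. What it estimates depends on how status is parameterised, which the plan leaves open.

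Two analysts could follow the text faithfully and report different changes, possibly with opposite signs, from the same data. The reported figure could also rest on the few patients who progressed or died by Day 56. The power statement refers to a different quantity, the mean change over all 37 patients. A reader would take the reported estimate to be the one that was powered.

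**Working it through.** **1. The plan's own figure.** Paired t-test, n = 37, shift 0.47 SD of the differences, alpha 0.05 two-sided (the plan does not state sidedness). Non-centrality = 0.47 × √37 = 2.859 on 36 df; power = 79.4%. The shift detectable at 80% is 0.473. The stated 80% therefore reproduces as a two-sided test of the mean change over all patients. A one-sided test would give 87.7%.

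**2. What the time parameter is.** Write the mean as β0 + β1·t + β2·s + β3·t·s, with t = 0 before and 1 after treatment and s the coded status. The change at status s is β1 + β3·s. Let Δ_E and Δ_N be the changes in the event and no-event strata, and p the event proportion.

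- Reference coding (s = 0 in the reference stratum): β1 = Δ_E or Δ_N, whichever stratum is the reference.
- Sum coding (s = ±0.5): β1 = (Δ_E + Δ_N)/2.
- Status centred at its sample proportion: β1 = p·Δ_E + (1 − p)·Δ_N, the all-patient change.

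With complete pairs, β1 thus equals the all-patient change if status is centred, if the strata are equal in size under sum coding, or if the observed stratum changes coincide.

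**3. Check on one simulated data set** (assumed split of 11 events and 26 no events; mixed model with random intercept). Observed changes were +0.363 (event) and −0.561 (no event).

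| Parameterisation | Fitted time parameter |
|---|---|
| No event as reference | −0.561 |
| Event as reference | +0.363 |
| Sum coding | (−0.561 + 0.363)/2 = −0.099 |
| Status centred | (26 × −0.561 + 11 × 0.363)/37 = −0.286 |

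The overall mean change was −0.286. The values illustrate the algebra and do not predict trial results.

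**4. Precision and power when both strata truly change equally.** Here every coding targets the same true value, so only precision differs. Assumptions: 6 events and 31 no events; measurement SD 1; correlation 0.2 (given in the plan only for the status-dependent case); true shift 0.60 measurement SD in both strata.

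SD of a difference = √(2 × (1 − 0.2)) = 1.265, so 0.60 is 0.60/1.265 = 0.47 SD of the differences, matching the plan's effect. Power is from the non-central t, 35 df, two-sided 0.05, without multiplicity adjustment.

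| Quantity | SE | 0.60/SE | Power |
|---|---|---|---|
| Event as reference | 1.265/√6 = 0.516 | 1.162 | 20% |
| No event as reference | 1.265/√31 = 0.227 | 2.641 | 73% |
| Sum coding | 0.5 × 1.265 × √(1/6 + 1/31) = 0.282 | 2.127 | 54% |
| Overall change | 1.265/√37 = 0.208 | 2.885 | 80% |

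From 4 to 8 events, power runs from 15% to 26% (event reference), from 75% down to 70% (no-event reference) and from 41% to 64% (sum coding). The overall change stays at 80%.

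**5. Is 6 events plausible?** The documents give no Day 56 split. With correlation 0.2, a 6/31 split gives SE of the interaction = 1.265 × √(1/6 + 1/31) = 0.564. Power for a 1.6 SD difference between strata is then 79%, close to the plan's 80%; a near-even split gives 96%. So 6 is compatible with the plan's figures but remains an assumption.

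**6. Does a non-significant interaction make this harmless?** At 6/31 the interaction test has 41% power for a 1.0 SD difference between strata and 14% for 0.5 SD. Non-significance would often coexist with strata that differ.

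**The case against.** The best defence is that the plan already separates two cases. If change depends on status, contrasts are taken within strata; if not, "this experiment can be considered as a paired t-test", which is the overall change. On that reading the reported time effect is the common one and only a clarifying phrase is missing. This stands in part: it supports the inference that the overall change is the intended target, which the section never says outright. It does not rescue the analysis as written, because the remark belongs to the power calculation and removes no term from the model.

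Other points on that side are sound and limit the claim:

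- A reader might infer that the time parameter can never be the all-patient change. That is false; step 2 gives three cases where it is. The plan specifies none of them, but its silence on coding does not exclude them.
- A reader might infer that the confidence interval is wrong. It is valid for the coefficient it accompanies; the question is which quantity that is.
- A reader might infer that the Hochberg procedure is run on the wrong test. Section 12.2 does not say which test enters it, so this cannot be asserted.
- The low 20% figure needs the event stratum as reference. With the no-event stratum as reference the loss is modest, 73% against 80%.

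**Conclusion.** The concern holds in a limited form. Followed as written, Section 12.2 reports a quantity set by an unstated coding, usually one stratum's change or an unweighted mean of two, while the power rests on the change over all 37 patients. Where the strata differ, the estimate answers a different question. Where they do not, it is unbiased but less precise, except in the special cases.

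The power losses are illustrative. They depend on the assumed event count, on carrying the 0.2 correlation into the case without status dependence, and on the coding chosen. The algebra depends on none of these.

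The gap bites when the interaction is not significant and the time parameter stands as the main immune result; otherwise the planned stratum contrasts are reported. Nothing here supports a wider inference: the analysis is correlative and does not touch the 24-week PFS decision rule or the Phase 2 sample size.

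**What to change.** In Section 12.2, replace the time parameter as the reported change with a pre-specified time contrast weighted by the observed status distribution, with its 95% confidence interval. Centring status at its sample proportion is equivalent. State which patients define the weights, since some may lack a Day 56 sample. State also that this contrast is the test entering the Hochberg procedure for the eight measurements.

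Keep the within-stratum contrasts when the interaction is significant. Do not make the overall estimate depend on refitting without the interaction after a non-significant test: that is a test-then-estimate rule resting on a weak test (step 6).

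The cost is a sentence or two of SAP text and one contrast statement. No extra data or patients are needed.

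### Section 12.2 ties stratum-specific immune changes to a significant status-by-time interaction, but that test would miss a 0.5 SD difference roughly 78% to 90% of the time

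*Combined protocol and SAP*

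**What the plan says.** Everything relevant is in section 12.2 of the combined protocol and SAP.

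- The mixed model for the baseline-to-Day-56 change has a random patient effect and fixed effects for time, "patient status at Day 56 (progression/death or not) and the status-by-time interaction".
- The default summary is a single parameter: "The magnitude, direction and reliability of the change estimate will be described using the fitted parameter estimate for time and its 95% confidence limits".
- Stratum results have a condition. Dependence on status is glossed, by an i.e., as a significant interaction: "if the status-by-time interaction is statistically significant), the change will be estimated and tested within progression strata using contrast statements".
- The power text uses the same two branches. Its inputs are: "we assume paired (pre/post) standardized observations are available for 37 patients, and significance threshold of 0.05". On the first branch, "If the change in immune measurements does not depend on progression status, then this experiment can be considered as a paired t-test", and the stated power is: "This test has 80% power to detect a 0.47 standard deviation shift in mean immune measurement". On the second, "we further assume a within-patient correlation coefficient of 0.2", and the model is said to give "80% power to detect a 1.6 standard deviation difference in the progression strata specific regression line slopes".

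The number of the 37 patients expected in the progression/death stratum is not given. No margin, and no confidence interval for the interaction, is planned for the case where the test is not significant.

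**The concern.** Status is in the model so that the trial can show whether immune change tracks outcome. Section 1.6.2 says that immune results will be correlated with patient outcome. Under the written rule, the stratum changes are planned outputs only when the interaction passes a significance test.

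Two things follow if that test has little power. First, failure to pass says almost nothing about whether the change differs by status, yet it decides whether the stratum changes are shown. Second, when the test does pass, the estimates are seen because they were large enough to pass, so they tend to overstate the difference. The plan's own figures raise the question: 0.47 SD is the detectable shift for the overall change, while the interaction needs 1.6 SD.

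**Working it through.** **Inputs from section 12.2:** 37 pre/post pairs; threshold 0.05 (taken as two-sided, which reproduces the stated power); within-patient correlation 0.2; 80% power at 0.47 SD (overall change) and at 1.6 SD (interaction). **Assumptions:** the stratum split, shown as a range, and 0.5 SD as the benchmark difference, chosen because it is close to 0.47. The plan sets no target for the interaction other than 1.6 SD.

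**1. Overall change.** Paired t-test, 36 df, noncentrality 0.47 × √37 = 2.86. Power is 79.4%, and 80% is reached at 0.473 SD. The plan's figure reproduces.

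**2. What the stated 1.6 SD implies, with no split assumed.** In the normal approximation, 80% power needs a difference of (1.960 + 0.842) = 2.80 standard errors. So SE = 1.6 / 2.80 = 0.571. For a true difference of 0.5 SD, 0.5 / 0.571 = 0.876, and power = Φ(0.876 − 1.960) + Φ(−0.876 − 1.960) = 0.14. The test misses 86%.

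**3. Rebuilding the interaction test.** With two time points, the interaction compares the mean change between strata. In units of the marker SD, the SD of the change is √(2 × (1 − 0.2)) = 1.265, and SE = 1.265 × √(1/n₁ + 1/n₂). Power comes from the noncentral t with 35 df (critical value 2.030).

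At 1.6 SD the power is 78.7% for a 6:31 split, 83.4% for 7:30 and 96.2% for 18:19. The plan's 80% therefore reproduces if about 6 of 37 patients are in the progression/death stratum.

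| Split | SE | Power at 0.5 SD | Missed at 0.5 SD | Missed at 1.0 SD | 95% CI half-width (2.030 × SE) |
|---|---|---|---|---|---|
| 3:34 | 0.7618 | 9.8% | 90.2% | 75% | 1.55 SD |
| 6:31 | 0.5642 | 13.9% | 86.1% | 59% | 1.15 SD |
| 18:19 | 0.4161 | 21.5% | 78.5% | 35% | 0.84 SD |

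**4. Other scale.** If 0.5 SD is read in units of the change score (SD of change = 1), the miss rate is 87.3% (3:34), 80.7% (6:31) or 68.5% (18:19).

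**5. Multiplicity.** Section 12.2 applies Hochberg to 8 measurements and does not say whether this covers the interaction tests. If it does, the strictest step is 0.05/8 = 0.00625, and the miss rate at 0.5 SD on the marker-SD scale is 94.5% (18:19) to 98.2% (3:34).

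**6. What a non-significant result can exclude.** Its 95% CI contains zero and, even at 18:19, is typically about 2 × 0.84 = 1.68 SD wide. One end must then lie at least 0.84 SD from zero, so a 0.5 SD difference in at least one direction stays inside the interval.

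**7. Selection after significance.** Mean estimated difference among significant results, by simulation on the marker-SD scale:

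| True difference | 6:31 | 18:19 |
|---|---|---|
| 0.5 SD | 1.33 SD (2.7-fold) | 1.04 SD (2.1-fold) |
| 1.0 SD | 1.5-fold | 1.2-fold |
| 1.6 SD | 1.13-fold | 1.02-fold |

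**The case against.** Much of the case on the other side stands, and it rules out several stronger readings.

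- **A reader might infer that the plan concludes independence when p > 0.05.** It does not say so. The rule states only what happens when the interaction is significant. The sentence about change not depending on status is a planning condition in the power paragraph. What the text supports is narrower: dependence is equated with significance, and nothing is planned for the other case.
- **A reader might infer that stratum results are withheld.** Nothing forbids them. Status and its interaction are in the model, so they are estimated whatever the p-value. Section 12.2 also has exploratory mixed models with status interactions and no significance condition. Those models use another status coding (progressed, died, other) and all three measurements, and they promise no stratum changes for the Day 56 comparison. Reporting is therefore not guaranteed, which is different from prohibited.
- **A reader might infer that one pooled change is reported.** The plan reports the time parameter and never says that the interaction is dropped. With the interaction retained, the meaning of that parameter depends on coding. A claim that a pooled interval misleads rests on that assumption and on which target is chosen. With a true 1.0 SD difference missed at 6:31, such an interval covers the 6-patient stratum's change only 3% of the time, but the 31-patient stratum's change about 89% and the average change about 96%.
- **A reader might infer that any significant result is exaggerated two- to three-fold.** That size belongs to a true difference of about 0.5 SD. At the plan's own 1.6 SD the exaggeration is small.
- **The plan is open about its sensitivity, and 0.5 SD is not its target for the interaction.** Both are true. Disclosing weak power does not make the same test a sound condition for reporting.
- **The analysis is correlative, and the added intervals will be wide.** Also true. It limits the weight of the point, but wide intervals are the accurate description of what 37 patients can show.

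**Conclusion.** The concern holds in limited form. A non-significant status-by-time interaction in this trial cannot support absence of dependence on status, and stratum results shown only after significance are a selected set.

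The plan's own 1.6 SD figure implies about 86% missed at 0.5 SD with no assumption about the split. Rebuilt from 37 patients and correlation 0.2, the miss rate is about 78% to 90% on the marker-SD scale and about 69% to 87% on the change-score scale. At 1.0 SD it is 35% (18:19) to 59% (6:31). These figures assume a two-sided 0.05 test, complete pairs for all 37 patients and a split that the plan does not state.

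The point concerns planned reporting in a correlative analysis. It does not affect the 24-week PFS decision. It should be changed because the change is cheap and removes a selection step.

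**What to change.** In section 12.2, remove the significance condition. For every immune measurement, report the baseline-to-Day-56 change in each status stratum, and the between-stratum difference in change, each with its 95% CI and whatever the interaction p-value. Add a sentence that a non-significant interaction is not evidence that the change is independent of status.

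The cost is SAP wording and a few table rows per measurement, with no extra patients, samples or visits. The drawback is that wide intervals become visible: a half-width for the difference of about 0.84 SD at 18:19 and 1.15 SD at 6:31.
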